### **4.3 Exclusion Criteria**

1. Prior use of Clickotine or QuitGuide.
2. Current use of pharmacotherapy for smoking cessation or nicotine replacement therapy (NRT).

### **4.4 Replacement of Subjects**

Drop-outs will not be replaced.

## **5. STUDY TREATMENTS**

### **5.1 Clickotine**

The intervention regimen around Clickotine® is almost entirely user-directed. When a person has a craving, a series of options are available to ease the craving and resist the urge to smoke. The user will also engage with Clickotine® leading up to their quit date to complete a program of 21 Missions, daily activities which help prepare them to quit and keep them off cigarettes. Ideally, the user will open and use Clickotine® several times a day.

### **5.2 National Cancer Institute's QuitGuide**

## **CONFIDENTIAL**

The QuitGuide (QG) app is operated by the National Cancer Institute to provide education and support to smokers seeking to quit. The QG regimen is entirely user-directed. When a user has a craving or wants support or education, they can log into the QG app. The QG app also provides lessons relevant for preparing to quit and beginning to quit.

### **5.3 Allocation to Treatment**

Eligible participants will be randomized, 1:1 ratio, to receive Clickotine or QuitGuide. Randomization will occur during the randomization call at which time of successful installation of the assigned application will be confirmed. The participate user ID is assigned prior to randomization.

### **5.4 Maintaining the Blind**

Subjects will be blinded to group assignment and will be hypothesis blind along with site investigators, as they will be informed that the study is investigating 2 different apps to treat smoking cessation that could both be effective. The study team will be blinded to participant group assignment, including the PI, biostatistician, and medical monitor, with the exception of the research coordinator who will need to be aware of group assignment in order to assign unique study IDs and offer technical assistance appropriate to the app assigned to participants.

### **5.5 Measures to Minimize Bias: Randomization and Blinding**

In order to minimize bias with randomization and blinding, the study sponsor “Click Therapeutics” will be masked and will not be revealed until after study completion of protocol # CT-101-002. This decision was made by the sponsor “Click Therapeutics” to avoid potential unblinding and study bias that could be caused by Click’s software “Clickotine” being used as the primary experimental arm for the CT-101-002 protocol. “My Digital Study” will be listed as the study sponsor at the start of the trial for all participants to properly ensure blinding is maintained. The sponsor will disclose “Click Therapeutics” as the study sponsor after study completion. Upon study completion, all study participants that were randomized into the clinical trial will be emailed or mailed documentation revealing the study sponsor as “Click Therapeutics” along with a brief explanation of the sponsor’s masking rationale. (See Appendix 12.7).

## **6. DEVICE SUPPLY**

### **6.1 Software Provision**

Once the participant is randomized, the investigator will make sure that the participant has properly downloaded the mobile applications necessary for their assigned treatment group. This will consist of the interventional applications, Clickotine or QuitGuide, and the iCO Smokerlyzer application. The participants are instructed to have their device fully charged and are encouraged to have wifi accessibility during the randomization phone call.

## **6.2 iCO Smokerlyzer**

Participants will receive an iCO Smokerlyzer to be used at the user's discretion periodically throughout the trial regardless of treatment group. At Week 4 (Day 28), participants will be asked to submit an exhaled CO assessment to ensure the Smokerlyzer works properly, to identify any issues and as an adherence check. At the time of the Outcome Survey, participants will be required to submit another exhaled CO assessment, which will be recorded as a study endpoint.

Upon completion of the Outcome Survey, participants will be invited to submit the CO assessment over a live video feed to confirm identity, until videos are received from 25 CKT users and 25 QG users. After 25 videos are received from each treatment group, participants will no longer be invited to submit the CO assessment over live video feed and will instead receive a reminder to remotely submit an exhaled CO assessment.

In order to conduct the CO assessment via live video monitoring, participants must have access to another device with video capabilities, such as another mobile device or computer. Participants that are invited to conduct the CO assessment via live video monitoring will consent to participate in live video monitoring at the end of the outcome survey by answering "Yes" or "No". Study participants that answer "Yes" and will then be linked to schedule a video call via Calendly with the research coordinator. Participants will have the option to select their preference of video platform on Calendly.

During the live video monitoring participants will be required to provide a personal ID to confirm identity. Participants who consent to participate in the live video CO assessment will receive an additional \$50 Amazon gift card for their participation.

Those who do not consent to participate in the live video monitoring CO assessment will receive a reminder to submit the end of study CO assessment.

## **6.3 Participant Follow-up Procedure**

## **CONFIDENTIAL**

In the event a participant does not complete a scheduled activity/assessment on the projected target date or within the protocol specific window (see protocol section 6.5: schedule of activities), the research coordinator will initiate 3 follow-up attempts via- SMS, email, or telephone. The follow-up SMS messages & Phone Call Voicemail dialogue can be found in appendix 15.11-15.12.

### **Baseline follow-up**

Day 1: 24 hours post baseline survey email: SMS Message & Email  
Day 3: 24 hours post baseline survey email: SMS Message & Email  
Day 5: Phone Call follow-up  
Day 8: Lost to Follow-up Letter (if baseline survey not completed by day)

### **Randomization follow-up (3 day window to schedule)**

Day 1 - Phone Call follow-up  
Day 4: Lost to follow-up letter

### **Smokerlyzer Confirmation Assessment Follow-up**

Day 29: SMS Message & Email  
Day 30: SMS Message & Email  
Day 31: Phone Call follow-up

### **End of Study follow-up**

Day 56: SMS Message & Email  
Day 57: SMS Message & Email  
Day 58: Phone Call follow-up

## **6.4 Permitted Concomitant Treatments**

To control for medication or NRT use, participants will not be eligible to enroll if they are currently using a medication or NRT at study enrollment.

Starting at Day 0 of the study, study participants will be allowed to choose to begin using a smoking cessation medication or NRT. Participants will be asked about medication or NRT use during the study in outcome survey.

## **6.5 Excluded Concomitant Treatments**

None.

## **6.6 Subject Completion and End of the Study**

Participants who continue with the study through its completion will spend a total of 8 weeks using CKT or QG. They will be declared officially finished with the study following an outcome

survey at the end of this period but can continue to use CKT or QG even after the study's official completion.

## **7. STUDY PROCEDURES**

*An overview of the procedures and time points for each procedure is depicted by the schedule of activities on Pages 19.*

### **7.1 Recruitment, Screening and Baseline Period**

Advertisements (See Appendix 15.18) will be placed on social media and sent to 11,000 participants in a Magellan Behavioral Health value-based care network. Respondents to the advertisements will be directed to a website that asks several questions to determine their eligibility to participate in the study (See Appendix 15.2). If answers indicate eligibility, the user will be prompted to review and sign the informed consent. Participants are instructed to contact the study coordinator via telephone or email to answer any questions that the participant has, and/or to further discuss the study prior to completing the online Informed Consent form. Upon completion of the online Informed Consent, a copy of the signed ICF will be provided to the participant.

After the informed consent is signed, each participant will be assigned a unique participant user ID that will be used for the duration of the study. Once participant user ID numbers have been assigned, they cannot be reassigned or reused for any reason. The investigator and research coordinator must maintain a log linking the participant user ID to the participant's name. The investigator and study coordinator must follow all applicable privacy laws in order to protect a participant's privacy and confidentiality.

After signing the online informed consent, participants will automatically receive the Baseline Survey via email. The online Baseline survey (See Appendix 15.7) must be completed within 7 days (*Ex. Criteria #3*) as the participant's personal Baseline survey link expires 1 week after the automated email is generated to the study participant. Please see Section 6.3 for the baseline follow-up attempt procedure. Participants who do not complete the Baseline Survey during the 7-day baseline period window will be considered a screen fail and discontinued from the study. Participants that are discontinued from the study will not be eligible for rescreening.

This questionnaire was constructed from several standard surveys measuring smoking and addiction behavior (Modified Cigarette Evaluation Questionnaire, Capelleri et. al 2007; Mood and Physical Symptom Scale, West and Hajek, 2004; Morisky Medication Adherence Scale, MMAS-4,

Morisky et. al 1986), as well as basic medical history and demographic questions for data purposes (Cappelleri, et. al, 2007)

Upon completion of the online informed consent and Baseline Survey, participants will be directed to schedule a telephone call via Calendly with the study coordinator for Randomization.

Participants will be given a three-day window to schedule the date for the Randomization phone call with the research coordinator., Participants who are not able to schedule the randomization call within the protocol window will be considered a screen failure and not included in the ITT sample.

## **7.2 Randomization**

Randomization to treatment arm will utilize a predetermined sequence for up to 195 participant enrolled in the study, balanced 1:1 CKT:QG, balanced in blocks of 4. The research coordinator will be the only study staff member with access to the randomization sequence and will assign participants to CKT or QG based on their position in the randomization sequence.

Randomization procedures will occur via telephone with the research coordinator to verify participant eligibility and confirm download of installed treatment arm application on the randomization date. In the case of technical error during the scheduled call or other need to reschedule, participants will have 1 business day to reschedule the randomization call with the research coordinator. If calls are not conducted within the protocol window, the participant will be considered a screen failure and not included in the ITT sample.

Participant study eligibility will be verified prior to randomization on the day of the scheduled telephone contact with the research coordinator. Once eligibility is confirmed, the research coordinator will facilitate randomization assignment into a treatment group of CKT or QG. The assigned treatment arm and Smokerlyzer application links will be emailed to the participant for downloading of CKT or QG.

The study intervention start **date/ day 0** will be on same day of randomization and confirmed installed treatment application of activated Clickotine or QuitGuide. Only randomized participants that are able to confirm download of assigned treatment arm will be included in the ITT sample.

In the event participants are randomized to a treatment group and unable to confirm successful download of assigned treatment application, they will be **excluded** from the study by (*Incl # 10*) and will **NOT** be included in the study ITT sample.

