#### **1.5 Rationale for Study Conduct**

This study is being conducted as per NIH(NIDA) Grant 1 R43 DA045395-01 “Clinical trial of an innovative digital therapeutic for smoking cessation with biochemical verification” to [name].

**Rationale:** The demonstration of CKT's efficacy in producing superior smoking cessation rates in a sample of Medicaid users with biochemical verification of cessation, accomplished through establishing feasibility of conducting the research in Phase 1 and conducting a large-scale trial in this sample in Phase II, are the next steps in the clinical validation and commercialization of the product.

**Comparison Arm:** The active comparator app, the National Cancer Institute (NCI)'s QuitGuide (QG) was selected in acknowledgement of the fact that placebo interventions cannot be implemented in digital interventions of this type. Treatment-as-usual comparators could

introduce a negative bias among subjects denied access to CKT, would not allow for any level of blinding, and are fundamentally difficult to implement in a remote, digital trial. QuitGuide is a widely used smoking cessation app which like, CKT, follows USPCG guidelines, and has published quit rates in a controlled clinical trial setting. As an NIH-developed tool whose content is based on Smokefree.gov, the most-accessed cessation website, subjects would have reasonable expectancy that QuitGuide would be at least as effective as CKT. For these reasons, QuitGuide is widely used as an active comparator, for example in a published RCT of smoking cessation apps (Iacoviello et al., 2017) and in the each of the trials of this type registered at ClinicalTrials.gov, NCT02930200 and NCT01982110.

**Randomization:** The investigators considered dynamic randomization to ensure that covariates which may affect quit rates are equally distributed between study groups but decided at this Phase I stage to examine the effects of these covariates in post hoc tests. Data from these secondary analyses will be used to inform the design of a dynamic randomization procedure for the Phase II research.

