## **CONFIDENTIAL**

4. Smokes at least 5 cigarettes daily.
5. Is interested in quitting smoking in the next 30 days.
6. The participant owns and has access to an iPhone with iOS 9 or greater capabilities, or an Android with OS 7 or greater capabilities.
7. The participant is willing and able to receive SMS text messages on their smartphone.
8. The participant is willing and able to receive email messages.
9. Ability to confirm download of installed treatment arm app via telephone on randomization date.
10. One half of the study sample will be recruited from the general population of smokers via social media advertisements.
11. One half of the study sample will be recruited via mail from a Magellan Behavioral Health value-based care network.

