### **10.3 Primary Endpoint**

The primary endpoint will be self-reported 30-day abstinence from smoking on the outcome survey as per Russell Standard Self- Reported 4-Week Quitter status.

30-day smoking cessation status (dichotomous variable: yes/no) will be compared between the CKT and QuitGuide groups utilizing logistic regression. Two-sided p-values will be calculated from logistic regression models, with adjustments to the models by: race, education, nicotine dependence, and living with a partner who smokes, consistent with previous studies' models.

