The purpose of this SBIR Phase 1 project is to demonstrate the efficacy of Clickotine (CKT) in producing long-term cigarette abstinence in a value-based care population served by Click Therapeutics, Inc.’s commercial partner Magellan Behavioral Health, and to demonstrate the ability to base reimbursement from CKT on remote biochemical verification of successful cigarette abstinence. To do so, this SBIR Phase 1 project will support a pilot blinded, randomized, controlled trial of CKT versus the NCI QuitGuide (QG) app to test the hypothesis that CKT will produce greater 30-day abstinence rates than QG after 8 weeks of use. To demonstrate the feasibility of evaluating CKT in a Magellan value-based care population, half the study sample will be recruited from a Magellan value-based care population. To demonstrate the ability to base reimbursement on remote biochemical verification of successful cigarette abstinence, concordance rates between self-reported cessation on the outcome survey and the exhaled CO monitor result will be investigated; video monitoring of a subset of the first 50 study completers (first 25 completers in both CKT and QG groups) submitting the exhaled CO assessment will be conducted to validate the remote CO monitoring process. Smokers that are currently using a pharmacotherapy or Nicotine Replacement Therapy (NRT, including e-cigarette use) at study enrollment will not be eligible to participate. However, since some users are expected to choose to begin using smoking cessation pharmacotherapy or NRT during their quit attempt, users will be permitted to begin using smoking cessation pharmacotherapy or NRT during the trial if they so choose. Secondary analysis of the subgroup of NRT/pharmacotherapy users will be conducted to compare cessation rates between the CKT+NRT group and the CKT-only group, to address expected med/NRT use during the trial and to confirm the initial trial result that CKT+NRT is not superior to CKT-alone.

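### Recruitment source is fixed at half payer mail and half social media, but it is not used in randomisation, the primary model or any planned summary, so nothing planned reports on the payer half

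*Protocol*

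**What the plan says.** Section 4.2 of the protocol (Inclusion Criteria, items 10 and 11) sets the mix as a quota: "One half of the study sample will be recruited from the general population of smokers via social media advertisements" and "One half of the study sample will be recruited via mail from a Magellan Behavioral Health value-based care network".

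Section 7.2 describes one predetermined list, "balanced 1:1 CKT:QG, balanced in blocks of 4". The coordinator "will assign participants to CKT or QG based on their position in the randomization sequence". No stratification factor is named.

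The primary logistic model (protocol and SAP 10.3, repeated in the SAP's Data Analysis Plan) is specified "with adjustments to the models by: race, education, nicotine dependence, and living with a partner who smokes, consistent with previous studies' models". Source is not among the covariates. The secondary analyses in section 10.4 are agreement between self-report and CO, that agreement with and without video monitoring, and CKT with NRT against CKT alone. None is by source.

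The reason for the payer half is worded in two ways. Protocol 2.2 makes it a secondary objective to show that CKT can feasibly be evaluated in this population, and 3.2 speaks of being able to enrol from the partner's network. The SAP's Summary of the protocol says the project is to "demonstrate the efficacy of Clickotine (CKT) in producing long-term cigarette abstinence in a value-based care population", and then separately mentions feasibility.

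On covariate balance in general, protocol 1.5 records that dynamic randomisation was considered and that the investigators "decided at this Phase I stage to examine the effects of these covariates in post hoc tests".

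**The concern.** Members of a payer plan reached by mail and people who answer a social-media advertisement may differ in their chance of quitting. The documents give no quit rates by source, so this is plausible but not established. A factor that the design fixes, and that is known before assignment, is normally either balanced at randomisation or carried into the analysis. Here it is neither.

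Two things are at stake. The smaller is precision: balance between arms within source is left to chance. The larger is that the payer population is given as a reason for the trial in both documents, yet every planned result is pooled over both sources. This includes concordance, whose threshold of more than 85% is linked to the payer by name in section 10.4.

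**Working it through.** **Inputs.** From protocol and SAP 10.5: 156 enrolled, 78 per arm, 30-day rates 26.2% (CKT) and 8.3% (QG), two-sided alpha 0.05, 85% power. From 4.2: half from each source, so 78 payer and 78 social media. Assumptions: the sources enrol mixed together, and quit rates differ between sources by 5 to 20 points.

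**The plan's own figure.** With the mean rate (0.262 + 0.083)/2 = 0.1725, the normal-approximation formula is

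n = [1.960·√(2 × 0.1725 × 0.8275) + 1.036·√(0.262 × 0.738 + 0.083 × 0.917)]² / 0.179² = 78.4,

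so 79 per arm. Power at 78 per arm is 84.8%. The logistic-regression formula gives 156.9 in total. The stated 78 per arm and 85% reproduce.

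**Imbalance in payer share.** Let X be the number of payer recruits in the CKT arm. Ignoring the blocks, X is hypergeometric (156 in all, 78 payer, 78 drawn). The difference in share is (2X − 78)/78.
- SD = (2/78)·√(78 × 0.5 × 0.5 × 78/155) = 8.0 points.
- At least 10 points (X ≤ 35 or X ≥ 43): probability 26.2%.
- At least 15 points (X ≤ 33 or X ≥ 45): probability 7.8%.

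A simulation of blocks of 4 with mixed accrual (50,000 runs) gives SD 8.1 points and probabilities of 26.8% and 8.1%. If one source enrols entirely before the other, the same blocks hold the difference to 2/78 = 2.6 points.

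**Effect on the estimate.** Shift in the crude difference = imbalance × gap in quit rate between sources.

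| Imbalance | Gap 5 points | Gap 10 points | Gap 20 points |
|---|---|---|---|
| 10 points | 0.5 | 1.0 | 2.0 |
| 15.4 points (95th percentile of the simulation) | 0.8 | 1.5 | 3.1 |

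The planned difference is 26.2 − 8.3 = 17.9 points. The top of the gap range cannot hold in both arms: with equal halves and an overall QG rate of 8.3%, the largest possible gap in that arm is 2 × 8.3 = 16.6 points, with the other half at zero.

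**With two lists.** Blocks of 4 within each source leave at most 2 participants unbalanced per source, so the payer shares differ by at most about 2/78 = 2.6 points among those randomised. The required sample size does not change. Participants dropped after assignment for failing to confirm the download (7.2) could disturb this slightly.

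**What the payer half can show.** With 78/2 = 39 per arm and the planned rates:
- Power is 55% (pooled z), 51% (Wald logit) or 47% (exact Fisher).
- The 95% CI half-width is 1.96·√(0.262 × 0.738/39 + 0.083 × 0.917/39) = 16.3 points, around a difference of 17.9.

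**Room in the model.** Expected quits are 78 × 0.262 + 78 × 0.083 = 20.4 + 6.5 = 26.9. Appendix 15.3 offers seven race and nine education options. Entered in full, these alone need 6 + 8 = 14 indicator terms; the plan does not say how they will be coded.

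**The case against.** The strongest reply is that simple blocked randomisation is valid in a trial of 156, and that leaving covariate balance to chance was a considered choice, recorded in 1.5 with the aim of informing Phase II. That stands as far as it goes. It would be wrong to read the absence of stratification as a general oversight, although 1.5 does not name source and the post hoc tests it promises do not appear in section 10.

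A reader might infer that imbalance by source biases the comparison. It does not: imbalance arising by chance is noise that the test's error rate already allows for. Race, education and nicotine dependence are in the model and may absorb part of any difference between sources. About three times in four the imbalance stays below 10 points.

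A reader might also infer that the trial fails its payer purpose altogether. The documents do not support that. The protocol's own objective (2.2, 3.2) is feasibility and ability to enrol, the SAP calls the trial a brief feasibility study, and enrolment counts by source would speak to that objective. The monthly reviews track recruitment and retention, though by arm at most and not by source. Only the SAP's efficacy wording is left without an analysis. For the feasibility objective, the gap is that section 10 names no summary and no criterion.

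Finally, splitting by source cannot establish efficacy in payer members at this sample size. That is correct, and it limits the remedy to description.

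**Conclusion.** The point holds as a minor, inexpensive improvement. It does not threaten the validity of the primary comparison.

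The imbalance is real but modest: about a 26% chance of at least 10 points and 8% of at least 15, given 78 per source and mixed accrual. Its effect, 0.5 to 2 points for a 10-point imbalance, rests on an assumed gap of 5 to 20 points that the documents neither give nor exclude, apart from the 16.6-point ceiling in the QG arm.

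The reporting gap matters more and needs no assumption. As written, no planned result describes the payer half, neither for the efficacy purpose in the SAP nor for the feasibility objective in the protocol.

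**What to change.** 1. Record source as an analysis variable. Protocol 11.1 takes the regression covariates from the two surveys, and none of the survey items reproduced in Appendices 15.3 and 15.4 asks for source. The advertisements in 15.18 carry different web addresses and may allow tracing, but no section says this will be done.
2. Randomise from two lists, payer mail and social media, each 1:1 in blocks of 4. If randomisation is complete, rely on adjustment alone.
3. Add source as one binary term to the primary model, and state compact codings for race and education.
4. Report enrolment, retention, CO submission, concordance and quit rates by arm within each source, with the risk difference and 95% CI for quitting. Label the table descriptive.
5. Reconcile the efficacy wording in the SAP's Summary of the protocol with protocol 2.2 and 3.2. If feasibility is the aim, state in section 10 which summary or criterion will answer it.

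Cost: a second list, one table and one more parameter in a model with about 27 expected quits, which is why race and education need to be kept compact. No extra participants are needed.

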#### **4.2 Inclusion Criteria**

Participant eligibility should be reviewed and documented by an appropriately qualified member of the investigator's study team before participants are included in the study. There must be evidence of a personally signed and dated informed consent document indicating that the participant has been informed of all pertinent aspects of the study prior to any study procedure being performed. Participants must be willing and able to comply with study procedures such as the outcome survey and exhaled CO assessment.

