## 7.7 Baseline Period (0-10 days prior to Randomization)

Once the personalized link to the baseline survey is sent to the participant, the participant has a 7-day window to complete the baseline survey and a 3-day window to complete a phone call with the research coordinator that is contingent upon completion of the baseline survey. This phone call serves as a secondary measure to confirm eligibility once more before participant can be randomized. Completion of the baseline survey will prompt the participant to schedule the randomization phone call with the study coordinator via Calendly.

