### **Step 1: Research coordinator confirms eligibility and randomizes**

- Study coordinator reviews baseline questionnaire answers with participant to confirm eligibility
- After study eligibility is confirmed, the study coordinator will randomize the participant into one of the two treatment groups (Clickotine or QuitGuide)
- The assigned treatment and iCO Smokerlyzer application links will be emailed to the participant for download. The study coordinator will provide step-by-step application download instructions for the participants over the phone call and explicitly written out in the email. The participants who are randomly assigned to Clickotine will receive an access code in the email that contains the application download instructions because Clickotine requires a valid access code for the user to partake in the program.

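### The only person with access to the randomisation list also confirms eligibility and assigns on the same call, and the plan describes nothing that hides the next arm from that person

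*Protocol*

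**What the plan says.** Protocol section 7.2 specifies a predetermined sequence, "balanced 1:1 CKT:QG, balanced in blocks of 4", sized for up to 195 participants. On access it says: "The research coordinator will be the only study staff member with access to the randomization sequence and will assign participants to CKT or QG". Assignment follows the participant's position in the sequence.

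The order on the call is stated in the same section: "Once eligibility is confirmed, the research coordinator will facilitate randomization assignment into a treatment group of CKT or QG". Section 7.7 says of this call: "This phone call serves as a secondary measure to confirm eligibility once more before participant can be randomized". Section 7.8, Step 1, gives both tasks to the coordinator, beginning with: "Study coordinator reviews baseline questionnaire answers with participant to confirm eligibility".

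Section 5.4 blinds the PI, biostatistician and medical monitor. The coordinator is the exception, partly in order to "offer technical assistance appropriate to the app assigned to participants". Section 5.5, on measures to minimise bias, deals only with masking the sponsor's name. The SAP's summary of the protocol says only that participants are randomly assigned.

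Neither document mentions a central system, sealed allocations, one-at-a-time release or an independent list holder. Neither says whether future entries can be seen or what fixes a participant's position. Consent pages were not available for this review; the sections where release would normally be described were.

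On a related matter, Protocol 7.2, 7.8 and 10.2 and SAP 10.2 limit the intention-to-treat set to randomised participants who confirm the download. That confirmation comes after the arm is known.

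**The concern.** Allocation concealment means that whoever decides on enrolment cannot know the next arm while deciding. Here one person has access to the list, makes the last eligibility check and assigns. Confirming eligibility first sets an order, but it does not hide the next entry from someone who can consult the list. Keeping the list from other staff protects their blinding; it does not address this.

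If the next arm can be known, enrolling a caller, declaring a screen failure or rescheduling can come to depend on it, even without intent. The arms could then differ in prognosis at baseline, and the primary comparison is a superiority claim on self-reported abstinence.

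The authors knew that prognosis matters: "The investigators considered dynamic randomization to ensure that covariates which may affect quit rates are equally distributed between study groups". They chose instead to examine such covariates post hoc, so balance rests on the unstratified blocked list and on adjustment for four covariates (Protocol 10.3).

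**Working it through.** **1. Plan's own figure.** Inputs (Protocol and SAP 10.5): 26.2% vs 8.3%, two-sided 0.05, 85% power, 78 per arm. The pooled two-proportion formula gives 78.4, so 79 per arm, with power 84.8% at 78. Exact enumeration with the logistic Wald test gives 85.2% at 78. The stated sample size stands, and this point does not change it.

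**2. Predictability in blocks of 4.** Across the 6 possible blocks there are 24 positions. With past arms known, the next arm is certain at 8/24 = 33% and the best guess is right at 17/24 = 71%. Both figures assume that position follows call order. If instead position follows an ID order set at consent, screen failures leave unseen slots. With 156/195 = 80% of slots seen (assumed at random), certainty falls to 0.8² × 1/3 = 21%. If the list itself can be read ahead, the next arm is always known.

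**3. Error rate by size of imbalance.** Exact two-binomial enumeration, unadjusted logistic Wald test, 78 per arm, tables with a zero cell counted as not significant. The null rate is assumed to be (26.2 + 8.3)/2 = 17.25% in both arms.

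| Shift (CKT up, QG down) | Rates | Two-sided error |
|---|---|---|
| none | 17.25 / 17.25 | 4.5% |
| 1 point each | 18.25 / 16.25 | 5.7% |
| 2 points each | 19.25 / 15.25 | 9.3% |
| 3 points each | 20.25 / 14.25 | 15.6% |

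**4. Refusals needed.** Assume two equal prognosis groups, 27.25% and 7.25%, and the next arm always known. A share r of the poorer group is refused when CKT is next, and of the better group when QG is next. Refusals = 156/(1 − r/2) − 156. The better group's share in CKT = 0.5/(1 − r/2).

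| r | Refusals | CKT / QG | Error |
|---|---|---|---|
| 0.10 | 8.2 | 17.78 / 16.72 | 4.8% |
| 0.20 | 17.3 | 18.36 / 16.14 | 6.0% |
| 1/3 | 31.2 | 19.25 / 15.25 | 9.3% |

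Reaching 10% takes about 33 refusals. With groups only 10 points apart, 31 refusals give 5.7%.

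**5. Past arms only.** Steering is confined to the certain third (52 positions) at r = 1/3. Refusals = 52/(5/6) − 52 = 10.4. Rates = (2 × 17.25 + 19.25)/3 = 17.92 and (2 × 17.25 + 15.25)/3 = 16.58. Error is 5.0%.

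**6. Room for refusals.** Planned losses are 195 − 156 = 39 from all causes. Then 31/39 = 80% and 17/39 = 44%.

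**7. Effect of adjustment.** Simulation, 20,000 runs, better group 60% vs 40% of the two arms: unadjusted 9.2%; 4.4% with the steered-on factor in the model; 9.7% with only four unrelated covariates in the model.

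**8. Download point.** Count non-downloaders as smokers and multiply both rates by (1 − d), with d assumed. Keeping 78 downloads per arm needs 78/0.95 ≈ 82 or 78/0.90 ≈ 87 randomised per arm, and power is 85.0% in both cases. If randomisation stops at 78 per arm, power is 82.8% at d = 5% and 80.0% at d = 10%.

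**The case against.** The best defence is that the eligibility decision leaves little room for discretion. Screening is online and mostly objective. Baseline answers are submitted before the call, and participants book their own slot within fixed windows. A discontinued participant cannot be rescreened. Section 4.2 adds: "Participant eligibility should be reviewed and documented by an appropriately qualified member". The analysis adjusts for race, education, nicotine dependence and a smoking partner. The refusals needed for a material effect would use most of the planned losses, which must also cover expired surveys, unscheduled calls, ineligibility and failed downloads.

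All of this stands, and it is why the risk is modest. None of it hides the next arm. The call still includes a review of the answers by the person with list access. Section 7.2 also allows rescheduling for reasons other than technical error, while the rule for list position is not given.

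A reader might infer that the list is open and the coordinator does see future assignments. The documents do not say so: access does not establish an open list, and the text is silent on visibility. What follows is only that concealment is not described and so not protected.

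**Conclusion.** The point holds as a gap in safeguards. One named role combines list access, the final eligibility check and assignment on one call, and no concealed release is described.

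The size is unknown, because all steering in the calculations is assumed. An error rate of about 9% needs three things together: a visible next arm, an unmodelled factor separating groups by about 20 points, and about 31 refusals out of 39 planned losses. No passage establishes that such a factor exists among the items reviewed on the call. With past arms only, and position in call order, the effect is negligible.

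It would be tempting to conclude that the comparison is biased or its error rate inflated. The documents support neither; they show an avoidable exposure. This is a cheap improvement that should be made.

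The download exclusion is a separate defect and adds no weight to the concealment point. A set that drops randomised participants after their arm is known is not intention-to-treat in the usual sense.

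**What to change.** In Protocol 5.4 and 7.2:

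1. Hold the list in a randomisation module, or as sequentially numbered sealed allocations prepared by someone who neither enrols nor analyses.
2. Release each arm only after the eligibility record is locked.
3. State the fixed order that sets list position, and state that future entries cannot be seen.

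If release was already concealed, a sentence saying how would settle the main point. Varying block sizes are optional: with sizes 4 and 6 the next arm is certain about 5% of the time instead of 33%, but the best guess is still right about 69% of the time instead of 71%.

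The cost is a one-time set-up and a wording change, plus NIDA prior approval if this counts as a significant change (Protocol 12.1). N and the call do not change, and the roles blinded in section 5.4 stay blinded.

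Separately, analyse all randomised participants. Extend to non-downloaders the rule in the SAP's Data Analysis Plan that counts non-response as smoking. Report download exclusions by arm with reasons; Protocol 9.2 already asks for drop-out reasons by arm, but it is unclear whether these screen failures are included. Power holds at about 85% if 78 downloads per arm are kept, and falls to about 83% or 80% (assumed 5% or 10% non-download) if randomisation stops at 156.
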